4.4.7. Treatment Compliance

All participants are to receive two doses of either the multicomponent meningococcal serogroup B vaccine (4CMenB or Bexsero) against GC or saline placebo as their study vaccination at day 1 and 29. Treatment compliance with study product will be defined as the participant receiving all assigned doses within the assigned visit windows. A participant is not in compliance with the protocol treatment if they miss at least one dose or receive at least one dose out of the visit window. When this happens, it will be recorded as a protocol deviation, and the participant will be excluded from the per-protocol population ([Section 6.3.2](#)).

4.5. Immunogenicity and Safety Variables

4.5.1. Immunogenicity Variables

See [Table 2](#) for the schedule of study procedures.

Immunogenicity testing will include antibody assays, cell-mediated immunity assays, and bacterial adhesion assays. Antibody assays will be performed to measure the IgG and IgA concentrations against GC antigens at mucosal sites (rectum, vagina, oropharynx) and in serum, serum IgG concentrations against *N. meningitidis* antigens by enzyme-linked immunosorbent assay (ELISA), and serum bactericidal antibody titers determined by assessing GC survival in the presence of a fixed concentration of human complement source and serially diluted sera in which complement has been heat inactivated. Cell-mediated immunity assays will be performed to measure frequencies and function of memory B cells (MBC) and peripheral blood T cells specific for GC and *N. meningitidis* antigens by ELISpot. Cell-mediated immunity assays will be performed to measure frequencies, phenotype and function of peripheral blood CD4+ and CD8+ T cells and rectal mucosal CD4+ and CD8+ T cells specific for GC antigens by intracellular cytokine staining (ICS). Similar assays will also be performed with peripheral blood CD4+ and CD8+ T cells specific for *N. meningitidis* antigens. A bacterial adhesion assay will be performed to measure the percent inhibition by mucosal antibodies of gonococcal adhesion to a ME180 human cervical cell line at Day 43 in each treatment group. Serum for systemic immunity assays will be collected at days 1 (pre-vaccination), 8, 15, 29, 36, 43, 57 and 181. Serum and mucosal (rectum, vagina, oropharynx) samples for antibody assays will be collected at days 1 (pre-vaccination), 29, 43, 57 and 181.

The immunogenicity variables are: Concentration of mucosal antibodies (IgG or IgA) against GC antigens at mucosal sites (rectum, vagina oropharynx) and serum antibodies (IgG or IgA) against GC antigens. These will be measured by ELISA from specimens collected at each visit (days 1, 29, 43, 57 and 181), and results will be reported as geometric mean titer and 95% confidence interval for each time point for the two treatment arms.

- Frequencies and function of memory B cells and T cells from peripheral blood for GC and *N. meningitidis* antigens will be measured at each visit with ELISpot. The frequencies (cell count) will be reported. Frequencies and function of CD4+ and CD8+ T cells specific for GC and *N. meningitidis* antigens from peripheral blood, and GC antigens from rectal mucosae. These will be measured at each visit with ICS. Cell frequencies will be reported.
- Serum bactericidal antibody against GC and *N. meningitidis* will be measured and reported as geometric mean titer and 95% confidence interval for each time point for the two treatment arms.
- Inhibition of bacterial adhesion to a human cervical cell line (ME180) by mucosal antibodies will be measured by bacterial adhesion assay, and geometric mean titer and 95% confidence interval at each time point for two treatment arms will be reported.
- Other exploratory Immunogenicity outcomes measured by ELISA, ELISpot, and bacterial adhesion assays will be reported similarly.

4.5.2. Safety Variables

Safety will be assessed throughout the study.

Reactogenicity will be measured by pre-vaccination reactogenicity assessment, evaluation of the vaccination site and AE/SAEs from the clinic and self-reported reactogenicity information in an electronic memory aid with a paper back up.

Safety will be assessed by the frequency and severity of any AE related to 4CMenB immunization through the end of the study, and any SAEs through the end of the study.

5. SAMPLE SIZE CONSIDERATIONS

A total of approximately 50 participants (maximal 60) will be enrolled and randomized to one of two study arms, 40 participants will be randomized to the 4CMenB arm and 10 participants to the placebo arm. The 4:1 allocation ratio was not selected based on any formal statistical criteria but instead was selected to maximize the number of participants administered 4CMenB, and thus maximize the amount of immunogenicity data collected on participants administered 4CMenB. Of the 50 participants, 20 participants will be enrolled into the Rectal Mucosal Biopsy Cohort. As with the overall sample size, this number was not selected based on any statistical criteria but was selected weighing the feasibility of enrolling participants who would consent to the biopsy procedure against ensuring ample data was collected via rectal mucosal biopsy as there are no data on the impact of 4CMenB on immunologic responses at the human mucosal surfaces where GC is typically encountered.

This study is not designed to formally test any hypotheses associated with the safety or immunogenicity data.

6. GENERAL STATISTICAL CONSIDERATIONS

6.1. General Principles

Unless otherwise specified, continuous variables will be summarized using the following descriptive statistics: n (non-missing sample size), mean, standard deviation, median, minimum and maximum. For some immunogenicity outcomes, the titers /frequencies will be summarized by geometric mean titer (GMT) /geometric mean titer frequencies and confidence interval (CI), fold change (rise or decline) from baseline will be calculated for the follow up immunogenicity outcomes. When calculating geometric mean, only non-zero values will be included. The frequency and percentages (based on the non-missing sample size) of observed levels will be reported for all categorical measures. Exact confidence intervals for binomial proportions will be computed for safety variables. In general, all data will be listed, sorted by Treatment group, and participant, and when appropriate by visit number within participant. All summary tables will be structured with a column for each Treatment in the order presented and will be annotated with the total population size relevant to that table/treatment, including any missing observations.

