4CMenB includes OMVs containing PorA serosubtype P1.4, as well as three recombinant protein antigens (neisserial adhesion A [NadA], factor H binding protein [FHbp] fusion protein, and neisserial heparin binding antigen [NHBA] fusion protein).[9] An analysis of gonococcal incidence following a 4CMenB vaccination campaign in one region of Quebec, Canada found a non-significant reduction in gonorrhea cases in the post-vaccination period,[10] supporting the findings from New Zealand, and suggesting that 4CMenB vaccine could protect against gonorrhea.

A recent study found a high level of amino acid sequence identity between the 4CMenB OMV antigens and those in the MeNZB OMV in the vaccine studied in New Zealand, and with OMV homologues in a laboratory strain of GC. The same study found that rabbits vaccinated either with MeNZB or the OMV component of 4CMenB raised antibodies against GC, and that 4CMenB vaccination in humans elicited serum antibodies against GC.[11] In contrast, another study found vaccination with a native OMV vaccine raised SBA responses against GC in mice, but 4CMenB vaccination did not elicit similar SBA responses in humans.[12]

Given the potential public health impact of an effective vaccine against gonorrhea, a better understanding of the immunologic responses to GC following 4CMenB vaccination is needed. Specifically, although two studies have characterized antibody responses against GC following 4CMenB in serum, gonorrhea is a mucosal disease. While there are studies looking at the ability of meningococcal serogroup B vaccines to

modulate human nasopharyngeal mucosal immunity to *N. meningitidis*, there are no data on the impact of 4CMenB on immunologic responses at the human mucosal surfaces where GC is typically encountered (urethra, rectum, cervix, and pharynx).

This is a mechanistic clinical trial to assess the systemic and mucosal immunogenicity of the multicomponent meningococcal serogroup B vaccine (4CMenB or Bexsero) against GC, using a placebo vaccine (normal saline) as a comparator, in healthy young adults.

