3.3.2. Immunogenicity Outcomes

In the primary, secondary, and exploratory outcomes, the GMT for Enzyme-Linked Immunosorbent Assay (ELISA) will be calculated for Days 1, 29, 43, 57 and 181 for each treatment arm. The GMT is defined as:

$$GMT = \sqrt[n]{X_1 * X_2 * X_3 * \dots * X_n}$$

In practice, it is the equivalent of: $GMT = \text{Exp}\{[\log(X_1) + \log(X_2) + \dots + \log(X_n)] / n\}$

Where the X_1, X_2, \dots, X_n are the titers for each participant at a certain timepoint. A sample SAS code for calculating the geometric mean and the 95% confidence interval is shown below.

```
proc surveymeans  
  data=data geomean;  
  var variable;  
  run;
```

The geometric mean fold rise (GMFR) for ELISA titers will be calculated for Days 29, 43, 57, and 181 compared to baseline titer in each study arm. The fold change for each participant at each timepoint is calculated first by dividing the follow-up titer by the baseline titer, then the geometric mean and 95% confidence interval will be calculated for each treatment arm at each timepoint.

Similarly, the ratio of serum to mucosal (rectal, vaginal, and oropharyngeal) IgG will be calculated at each time point. The geometric mean and confidence interval will be calculated as above.

Percent inhibition of gonococcal adhesion to human cervical cell line by mucosal antibody is defined as:

$$100\% * [(Titer \text{ without mucosal antibody} - Titer \text{ with mucosal antibody}) / Titer \text{ without mucosal antibody}]$$

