8.3. Exploratory Outcome Analyses

For the exploratory outcomes, summaries of IgG antibody concentrations (GMT) at each time point and GMFR in each treatment group are shown in [Table 18](#), [Table 19](#), [Table 20](#), and [Table 21](#). Summaries of the ratio of serum to mucosal IgG GMT results will be presented in [Table 22](#) and [Table 23](#). Summaries of pairwise ratios of mucosal IgG concentrations among anatomical sites will be generated at each time point and presented in [Table 24](#) and [Table 25](#). Summaries of IgA antibody concentrations and serum bactericidal antibody (GMT) at each time point and GMFR for other exploratory outcomes are shown starting in [Table 26](#) and concluding with [Table 33](#). Serum Bactericidal Antibody GMT and GMFR will be presented in [Table 34](#).

Summaries of the frequency of antigen-specific immune cells will include the mean if data are reported as percentage, or geometric mean if data are reported as cell count per million cells. The corresponding 95% confidence interval as well as the median, minimum, and maximum values will be presented. Fold rise from baseline will be summarized by arithmetic, geometric mean^[2] or median. The summary of frequencies will be presented starting in [Table 35](#) and concluding with [Table 45](#). Figures depicting the GMT (IgG, IgA) or frequency (MBC, T cells) for each assay over time will be presented beginning with [Figure 10](#) and continuing through [Figure 39](#) (GMTs), and [Figure 74](#) to [Figure 87](#) (frequencies). Reverse cumulative distribution (RCD) plots will be presented with separate panels for each visit, and separate curves within each panel for

each study arm and overall. Antibody titers are shown beginning with **Figure 40** and continuing through **Figure 73**. Percent inhibition of gonococcal adhesion to human cervical cell line (ME180) by mucosal antibodies at day 43 in each treatment group will be show in **Table 46**. The results for each participant at each visit are listed in **Listing 11** through **Listing 22**.

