14.1.3 Prior and Concurrent Medical Conditions

Table 13: Summary of Participants with Pre-Existing Medical Conditions by MedDRA System Organ Class and Treatment Group

MedDRA System Organ Class	4CMenB (N=X)		Placebo (N=X)		All Participants (N=X)	
	n	%	n	%	n	%
Any SOC	x	xx	x	xx	x	xx
[SOC 1]						
[SOC 2]						

Notes: n = Number of participants reporting medical history within the specified SOC. A participant is only counted once per SOC.
 N = Total number of participants in each group.

Table 14: Primary Outcome - Rectal Mucosal IgG GMT and GMFR Results by Analysis Population, Time Point, and Treatment Group

Population	Time Point	Statistic	4CMenB		Placebo	
			OMV Ng 1291	OMV Ng CNG20	OMV Ng 1291	OMV Ng CNG20
Immunogenicity Population	Day 1	N	x	x	x	x
		GMT (95% CI)	x (x, x)	x (x, x)	x (x, x)	x (x, x)
	Day 29	N	x	x	x	x
		GMT (95% CI)	x (x, x)	x (x, x)	x (x, x)	x (x, x)
		GMFR (95% CI)	x (x, x)	x (x, x)	x (x, x)	x (x, x)
	Day 43	N	x	x	x	x
		GMT (95% CI)	x (x, x)	x (x, x)	x (x, x)	x (x, x)
		GMFR (95% CI)	x (x, x)	x (x, x)	x (x, x)	x (x, x)
	Day 57	N	x	x	x	x
		GMT (95% CI)	x (x, x)	x (x, x)	x (x, x)	x (x, x)
		GMFR (95% CI)	x (x, x)	x (x, x)	x (x, x)	x (x, x)
	Day 181	N	x	x	x	x
		GMT (95% CI)	x (x, x)	x (x, x)	x (x, x)	x (x, x)
		GMFR (95% CI)	x (x, x)	x (x, x)	x (x, x)	x (x, x)
Per-Protocol Population	Day 1	N	x	x	x	x
		GMT (95% CI)	x (x, x)	x (x, x)	x (x, x)	x (x, x)
	Day 29	N	x	x	x	x
		GMT (95% CI)	x (x, x)	x (x, x)	x (x, x)	x (x, x)
		GMFR (95% CI)	x (x, x)	x (x, x)	x (x, x)	x (x, x)
	Day 43	N	x	x	x	x
		GMT (95% CI)	x (x, x)	x (x, x)	x (x, x)	x (x, x)
		GMFR (95% CI)	x (x, x)	x (x, x)	x (x, x)	x (x, x)
	Day 57	N	x	x	x	x
		GMT (95% CI)	x (x, x)	x (x, x)	x (x, x)	x (x, x)
		GMFR (95% CI)	x (x, x)	x (x, x)	x (x, x)	x (x, x)
	Day 181	N	x	x	x	x
		GMT (95% CI)	x (x, x)	x (x, x)	x (x, x)	x (x, x)
		GMFR (95% CI)	x (x, x)	x (x, x)	x (x, x)	x (x, x)

Note: N = Number of participants in the Immunogenicity Population for Rectal Mucosal data for a specific assay (OMV1291, and OMV20) at each time for certain Treatment Group

Table 15: Rectal Mucosal IgG GMT and GMFR Results by Analysis Population, Time Point, Sex and Treatment Group

			4CMenB				Placebo			
			Female		Male		Female		Male	
Population	Time Point	Statistic	OMV 1291	OMV CNG20						
Immunogenicity Population	Day 1	N	x	x	x	x	x	x	x	x
		GMT (95% CI)	x (x, x)	x (x, x)						
	Day 29	N	x	x	x	x	x	x	x	x
		GMT (95% CI)	x (x, x)	x (x, x)						
		GMFR (95% CI)	x (x, x)	x (x, x)						
	Day 43	N	x	x	x	x	x	x	x	x

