			Day 1	Day 8	Day 15	Day 29	Day 36	Day 43	Day 57	Day 1	Day 8	Day 15	Day 29	Day 36	Day 43	Day 57
Immunogenicity Population	IFNg NZ98 OMV	N	x	x	x	x	x	x	x	x	x	x	x	x	x	x
		Geometric Mean	x	x	x	x	x	x	x	x	x	x	x	x	x	x
		95% CI	(x, x)	(x, x)	(x, x)	(x, x)	(x, x)	(x, x)	(x, x)							
	IFNg Ng1291 OMV	N	x	x	x	x	x	x	x	x	x	x	x	x	x	x
		Geometric Mean	x	x	x	x	x	x	x	x	x	x	x	x	x	x
		95% CI	(x, x)	(x, x)	(x, x)	(x, x)	(x, x)	(x, x)	(x, x)							
	IFNg CNG20 OMV	N	x	x	x	x	x	x	x	x	x	x	x	x	x	x
		Geometric Mean	x	x	x	x	x	x	x	x	x	x	x	x	x	x
		95% CI	(x, x)	(x, x)	(x, x)	(x, x)	(x, x)	(x, x)	(x, x)							
Per-protocol Population	IFNg NZ98 OMV	N	x	x	x	x	x	x	x	x	x	x	x	x	x	x
		Geometric Mean	x	x	x	x	x	x	x	x	x	x	x	x	x	x
		95% CI	(x, x)	(x, x)	(x, x)	(x, x)	(x, x)	(x, x)	(x, x)							
	IFNg Ng1291 OMV	N	x	x	x	x	x	x	x	x	x	x	x	x	x	x
		Geometric Mean	x	x	x	x	x	x	x	x	x	x	x	x	x	x
		95% CI	(x, x)	(x, x)	(x, x)	(x, x)	(x, x)	(x, x)	(x, x)							
	IFNg CNG20 OMV	N	x	x	x	x	x	x	x	x	x	x	x	x	x	x
		Geometric Mean	x	x	x	x	x	x	x	x	x	x	x	x	x	x
		95% CI	(x, x)	(x, x)	(x, x)	(x, x)	(x, x)	(x, x)	(x, x)							

Note: N is the number of participant in each treatment group at certain timpoint

The frequencies are measured as Spots per million PBMC, format is 0 - xxxx

Table 37: Frequencies of Peripheral Blood T Cells Specific for NHBA Antigens by Time Point and Treatment Group

Population	Assay: IFNg ELISpot	Statistic	4CMenB			Placebo		
			Day 1	Day 15	Day43	Day 1	Day 15	Day43
Immunogenicity Population	NZ98 NHBA Peptide pool	N	x	x	x	x	x	x
		Geometric Mean	x	x	x	x	x	x
		95% CI	(x, x)	(x, x)	(x, x)	(x, x)	(x, x)	(x, x)
	1291 NHBA Peptide pool	N	x	x	x	x	x	x
		Geometric Mean	x	x	x	x	x	x
		95% CI	(x, x)	(x, x)	(x, x)	(x, x)	(x, x)	(x, x)
	CNG20 NHBA Peptide pool	N	x	x	x	x	x	x
		Geometric Mean	x	x	x	x	x	x
		95% CI	(x, x)	(x, x)	(x, x)	(x, x)	(x, x)	(x, x)
Per-Protocol Population	Consensus Peptide pool	N	x	x	x	x	x	x
		Geometric Mean	x	x	x	x	x	x
		95% CI	(x, x)	(x, x)	(x, x)	(x, x)	(x, x)	(x, x)
	NZ98 NHBA Peptide pool	N	x	x	x	x	x	x
		Geometric Mean	x	x	x	x	x	x
		95% CI	(x, x)	(x, x)	(x, x)	(x, x)	(x, x)	(x, x)
	1291 NHBA Peptide pool	N	x	x	x	x	x	x
		Geometric Mean	x	x	x	x	x	x
		95% CI	(x, x)	(x, x)	(x, x)	(x, x)	(x, x)	(x, x)
	CNG20 NHBA Peptide pool	N	x	x	x	x	x	x
		Geometric Mean	x	x	x	x	x	x
		95% CI	(x, x)	(x, x)	(x, x)	(x, x)	(x, x)	(x, x)
	Consensus Peptide pool	N	x	x	x	x	x	x
		Geometric Mean	x	x	x	x	x	x
		95% CI	(x, x)	(x, x)	(x, x)	(x, x)	(x, x)	(x, x)

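### SAP 6.1 drops zero results from every geometric mean, which inflates the mean wherever zeros occur and removes the same participants from the fold rise

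*SAP*

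**What the plan says.** The rule is in SAP 6.1 (General Principles): "When calculating geometric mean, only non-zero values will be included". It names no assay, and no later section limits it.

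SAP 3.3.2 defines the GMT as the nth root of n values that "are the titers for each participant at a certain timepoint", with no exclusion. For fold rise it says: "The fold change for each participant at each timepoint is calculated first by dividing the follow-up titer by the baseline titer". The geometric mean and 95% CI of those ratios follow.

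SAP 8.3 uses geometric means for cell counts per million, and the note to Table 36 (T-cell ELISpot, geometric mean and CI) reads: "The frequencies are measured as Spots per million PBMC, format is 0 - xxxx". Table 37 has the same note. Table 34 plans bactericidal GMT and GMFR.

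Protocol 10.5.3 specifies log10 transformation and no imputation of missing values. It has no rule for zero or below-limit results. Neither document gives a detection limit or a substitution value.

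**The concern.** Discarding a zero conditions the summary on the outcome. Each arm's geometric mean then describes only participants with a detectable result, and that set differs by arm and visit, so randomisation no longer protects the comparison. If zeros are commoner on placebo, its mean rises most and the vaccine-placebo difference will usually be understated.

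Fold rise is hit at both ends. From zero to positive, the ratio is undefined. From positive to zero, the ratio is 0, which 6.1 removes. Those who go from undetectable to detectable are arguably the responders of most interest, and they vanish.

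The tables would not show the loss. N in Table 14 is the "Number of participants in the Immunogenicity Population for Rectal Mucosal data for a specific assay", counted by visit and arm. It is not the number of values averaged, and the shell has no row for zeros removed. With no hypothesis test planned, these means and intervals are the trial's result.

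**Working it through.** **Spread, from protocol Table 2 (Ng OMV, 40/10).**
- Placebo: 34297 (20947, 56156). ln-SD = ln(56156/34297) × √10 / 2.262 = 0.689.
- Vaccine: 42224 (36161, 49303). ln-SD = ln(49303/42224) × √40 / 2.023 = 0.485.
- Check: pooled SD = √[(39 × 0.485² + 9 × 0.689²)/48] = 0.529; SE = 0.529 × √(1/40 + 1/10) = 0.187. The ratio is exp(0.208 ± 2.011 × 0.187) = 1.23 (0.85, 1.79), as the protocol states.

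These are serum values. Applying them to other specimens is an assumption, and every zero share below is also an assumption.

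**Inflation of one GMT.** If a share f of a lognormal distribution falls below the limit and is reported as zero, the non-zero GMT is too high by exp{SD × φ(z)/(1 − f)}, with z = Φ⁻¹(f). At SD 0.689:

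| Zeros | φ(z)/(1 − f) | Inflation | Coverage of nominal 95% CI, n = 10 |
|---|---|---|---|
| 10% | 0.195 | 1.14 | about 93% |
| 20% | 0.350 | 1.27 | about 85% |
| 30% | 0.497 | 1.41 | about 72% |
| 50% | 0.798 | 1.73 | about 38% |

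Coverage is simulated.

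**Vaccine-placebo ratio** (implicit in the stated comparison, though the SAP tabulates no such ratio). Thirty percent placebo zeros put the limit at −0.524 × 0.689 = −0.361 on the ln scale, relative to the placebo GMT.
- True ratio 2.0, SD 0.689 in both arms. Vaccine z = (−0.361 − 0.693)/0.689 = −1.53, so 6% zeros and inflation 1.095. The rule gives 2.0 × 1.095/1.408 = 1.56. Setting zeros to half the limit gives 2.11.
- Table 2 ratio 1.23, vaccine SD 0.485. Vaccine z = (−0.361 − 0.208)/0.485 = −1.17, so 12% zeros and inflation 1.117. The rule gives 1.23 × 1.117/1.408 = 0.98; half-limit gives 1.26.
- Simulated 40/10 trials, true ratio 2.0, 30% placebo zeros: rule 1.58, half-limit 2.13, censored-data model 2.03.

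**Fold rise** (simulated pairs, both values detectable; within-person correlation 0.5 or 0.8).
- A true rise of 2.0 with 30% baseline zeros reads 1.74 or 1.88.
- A true fall to 0.50 with 10% baseline and 39% follow-up zeros reads 0.59 or 0.54.

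**Chance of at least one zero among 10 placebo participants.** At a 10% zero share, 1 − 0.9¹⁰ = 65%; at 30%, 1 − 0.7¹⁰ = 97%.

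**Bactericidal titers.** If 90% had no baseline titer, GMFR would rest on at most about 40 × 0.1 = 4 vaccine and 10 × 0.1 = 1 placebo participants. If 50% had none, it would rest on 20 and 5.

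**ELISpot-type counts** (Poisson-lognormal, ln-SD 1.0, true ratio 3.0, zeros 51% placebo and 23% vaccine). The rule gives 1.64. Setting zeros to half the smallest step gives 2.03, so substitution alone is not enough there.

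**The case against.** **Zeros are documented only for an exploratory assay.** This stands. T-cell ELISpot goes to the CSR addendum, and memory B cell and ICS tables use means and medians that the rule does not touch. Serum OMV IgG, with a planning placebo GMT of 34297, should have no zeros; whether rectal IgG can is not stated. For bactericidal titers the SAP says only that "4CMenB vaccination did not elicit similar SBA responses in humans", which does not establish that non-responders are recorded as zero. The effect on primary and secondary results is therefore unknown and may be nil.

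**Harm is small when zeros are rare.** Also true: coverage is close to nominal at 5% to 10%.

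**SAP 6.1 only supplies what 3.3.2 needs, since log(0) is undefined.** Some rule is indeed needed, but this one answers by deletion, whereas 3.3.2 counts every participant's titer. The conflict is arguable; the selection is not.

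**A zero baseline breaks the ratio whatever 6.1 says.** Correct, so deleting the sentence without a substitution rule would not be enough. For cell frequencies, 8.3 leaves the fold-rise summary open ("Fold rise from baseline will be summarized by arithmetic, geometric mean", or median), but a zero baseline is undefined under each.

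**Zeros remain visible.** The CSR will list excluded observations, Listing 9 gives individual rectal titers, and reverse cumulative plots are planned. SAP 8.3 also promises summaries that would retain zeros: "The corresponding 95% confidence interval as well as the median, minimum, and maximum values will be presented". These help the reader but do not correct the GMT, GMFR or interval, and the median and range are missing from the Table 36 and 37 shells.

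**Half-limit substitution is itself approximate.** It is, as the ELISpot figures show, which is why a model-based sensitivity analysis belongs beside it.

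**Conclusion.** The rule is wrong as written and should be changed before database lock. Its direction is certain for any single geometric mean: excluding zeros gives a higher value than keeping them at any positive value below the non-zero mean. It does not follow that the vaccine is favoured. More zeros on placebo pull the between-arm contrast down, and GMFR can move either way.

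The size cannot be fixed from the documents. On the borrowed serum spread, the distortion of the placebo GMT runs from 14% at 10% zeros to 73% at 50%, and interval coverage deteriorates markedly from about 20% zeros upward. Confidence is high about the rule and its mechanism; the effect on the primary outcome remains open.

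**What to change.** Delete the sentence in SAP 6.1 and replace it with a rule along these lines:

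> A result of zero or below the limit is a measured result, not missing data. Before log10 transformation it is set to half the limit of detection (ELISA, bactericidal assay) or half the smallest reportable frequency (ELISpot). Limits are listed by assay, antigen and specimen before database lock. All participants with a result stay in the GMT and GMFR, and N is the number of values used. The number and percent below the limit are shown by arm and visit. Where many values are below the limit (for example, more than 20% in either arm), a censored-data model (ELISA, bactericidal assay) or a count model (ELISpot) is added as a sensitivity analysis.

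The 20% trigger is a convention; another threshold would do if fixed in advance. Align 3.3.2 with the new rule, and add the median, minimum and maximum to the Table 36 and 37 shells.

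The cost is SAP wording, one extra row per table, the sensitivity model where triggered, and a list of limits from the laboratory. It does not breach SAP 6.5, which bars imputing missing values, because a zero is not missing.
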